7.3 Follow-up Visits

Table 6: Mid-Study-Period Visit

Mid-Study-Period Visit					
(3-Week Visit, 10-Week Visit, and 17-Week Visit)					
Component	Procedure/Analysis				
Administrative	Review/update locator information				
	Schedule next study visit				
	Provide reimbursement for study visit				
Clinical	Collect interval medical/menstrual history				
	Review/update concomitant medications				
	 Record/update adverse events 				
	Perform physical exam (See Appendix III)				
	Perform pelvic exam (See Appendix III)				
	 *Treat for UTI/RTIs/STIs, treat or refer for other findings 				
	Reinforce counseling				
	o Contraceptive				
	 HIV/STI risk reduction and male condom 				
	 Protocol adherence, product use/adherence 				
	 Provide male condoms, offer panty liners 				
	*Provide watch device				
Behavioral	Administer behavioral assessment				
Urine	Collect urine sample				
	 Qualitative hCG 				
	 *Dipstick UA (*and culture if positive for leukocyte esterase or 				
	nitrates; may omit if culture not standard of care for UTI diagnosis)				
	 *SDA for chlamydia and gonorrhea 				
Blood	- Collect blood				
	Collect blood O Liver function tests				
	 Serum chemistries 				
	o Tenofovir				
	 *Syphilis serology (confirmatory tests as needed) 				
	∘ *HBsAg				
Pelvic	*Collect vaginal pH				
Specimens	 Collect vaginal pri *Collect vaginal fluid for wet mount (BV, Candida, Trichomonas) 				
	 Collect vaginal huld for wet mount (BV, Candida, Thenomonas) *Collect herpes culture (at sites where standard of care for diagnosis) 				
Study Product					
Supply	Collect unused study product (gel and/or tablets)				
	 Appropriate number of doses of study product(s) 				
*If indicated (see also					

*If indicated (see also MTN-001 SSP Manual)

Table 7: End of Study Period Visit

End of Study Pe (6-Week Visit, 13	riod Visit 3-Week Visit and 20-Week Visit)
Component	Procedure/Analysis
Administrative	 Review/update locator information Schedule next study visit Provide reimbursement for study visit
Clinical	 Collect interval medical/menstrual history Review/update concomitant medications Record/update adverse events Perform physical exam (See Appendix III) Perform pelvic exam (See Appendix III) *Treat for UTI/RTIs/STIs, treat or refer for other findings Reinforce counseling Contraceptive HIV/STI risk reduction and male condom Protocol adherence
Benavioral	Administer behavioral assessment
Urine	 Collect urine sample Qualitative hCG *SDA for chlamydia and gonorrhea *Dipstick UA (*and culture if positive for leukocyte esterase or nitrates; may omit if culture not standard of care for UTI diagnosis)
Blood	 Insert lock for specimen collection (may be omitted for non-intensive PK) Collect blood specimens (see also Section 7.8 for time points) Pre-dose Liver function tests Serum chemistries Flow cytometry (at sites with capacity) Tenofovir Plasma for storage Peripheral blood mononuclear cells (PBMC) for intracellular tenofovir diphosphate (sites with capacity) Post-dose Tenofovir PBMC for intracellular tenofovir diphosphate (sites with capacity) *Syphilis serology (confirmatory tests as needed) *HBsAg *Remove lock after specimen collection completed (as indicated)
	(CONTINUED)

Component	Week Visit and 20-Week Visit) (CONTINUED FROM PREVIOUS PAGE) Procedure/Analysis					
Pelvic						
Specimens	 Collect vaginal pH Collect vaginal fluid for wet mount (BV, Candida, Trichomonas) Collect CVL for vaginal flora proteomics, markers of inflammation, and tenofovir level (see also Section 7.8 for time points) Intensive PK/Sub-study ONLY (see also Section 7.8 for time points) Collect cervical cytology brush for tenofovir Collect vaginal biopsies for tenofovir *Collect herpes culture (at sites where standard of care for diagnosis) 					
Study Product Supply	 Collect unused study product (gel and/or tablets) *Dispense observed dose(s) of study product(s) (if participant does not bring sufficient unused study product to visit for use as observed dose(s), study product(s) will be dispensed to participant during the study visit) 					

*If indicated (see also MTN-001 SSP Manual), **Intensive PK/Sub-study (US sites) participants only (see also Section 7.8)

Table 8: 7-Week and 14-Week Study Visit

Г

7-Week and 14-Week Study Visits (Study Period 2 Start, Study Period 3 Start)					
Component	Procedure/Analysis				
Administrative	 Review/update locator information Schedule next study visit Provide reimbursement for study visit 				
Clinical	 Collect interval medical/menstrual history Review/update concomitant medications Record/update adverse events Perform physical exam (See Appendix III) Perform pelvic exam (See Appendix III) *Treat for UTI/RTI/STIs, treat or refer for other findings Reinforce counseling Contraceptive HIV/STI risk reduction and male condom Protocol adherence, product use/adherence Provide male condoms, offer panty liners Provide HIV pre- and post-test counseling 				
Urine	 Collect urine sample Qualitative hCG *Dipstick urinalysis (*and culture if positive for leukocyte esterase or nitrates; may omit if culture not standard of care for UTI diagnosis) *SDA for chlamydia and gonorrhea 				
Blood	 Collect blood specimens Complete blood count Liver function tests Serum chemistries HIV-1 test (confirmatory tests as needed) *Syphilis serology (confirmatory tests as needed) *HBsAg 				
Pelvic	 *Collect vaginal pH *Collect vaginal fluid swab for wet mount for BV, Candida, Trichomonas *Collect herpes culture (at sites where standard of care for diagnosis) 				
Study Product Supply	 *Collect any unused study product (gel and/or tablets) Dispense appropriate number of doses of study product(s) MTN-001 SSP Manual)				

*If indicated (see also MTN-001 SSP Manual)

Table 9: 21-Week Visit

21-Week Visit (Study Termination Visit)					
Component	Procedure/Analysis				
Administrative	 Review/update locator information *Schedule next study visit Provide reimbursement for study visit 				
Clinical	 Collect interval medical/menstrual history Review/update concomitant medications Record/update adverse events *Perform physical exam (See Appendix III) *Perform pelvic exam (See Appendix III) *Treat UTI/RTIs/STIs, treat or refer for other findings Provide HIV pre- and post-test counseling Reinforce counseling Contraceptive HIV/STI risk reduction and male condom 				
Behavioral	Conduct in-depth interview (subset of participants, see Section 7.7)				
Urine	 Collect urine sample Qualitative HCG *Dipstick urinalysis (*and culture if positive for leukocyte esterase or nitrates; may omit if culture not standard of care for UTI diagnosis) *SDA for chlamydia and gonorrhea 				
Blood	 Collect blood specimens Complete blood count Liver function tests Serum chemistries HIV-1 test (confirmatory tests as needed) Plasma for storage *Syphilis serology (confirmatory tests as needed) *HBsAg 				
Pelvic	 *Collect vaginal pH *Collect vaginal fluid swab for wet mount for BV, Candida, Trichomonas *Collect herpes culture (at sites where standard of care for diagnosis) 				
Study Product Supply	*Collect any unused study product (gel and/or tablets) MTN-001 SSP Manual)				

*If indicated (see also MTN-001 SSP Manual)

7.4 Follow up Procedures for Participants who Discontinue Study Product

Participants who discontinue study product will be encouraged to remain in the study if they are willing, for safety evaluations according to the study follow up schedule with the exceptions described below.

7.4.1 Participants Who Seroconvert to HIV

Study staff will capture seroconversions on study CRFs. As discussed in Section 13.9.2, participants may be offered participation in the MTN Seroconverter Study (MTN-015). Protocol-specified procedures will continue except:

- HIV serology
- All PK assessments
- Provision of study gel
- Provision of study tablets
- Product use/adherence counseling
- Counseling for HIV/STI risk reduction. Counseling will be modified to address primary and secondary HIV/STI prevention for infected women.

7.4.2 Participants Who Become Pregnant

All protocol-specified study procedures will continue except:

- Provision of study gel
- Provision of study tablets
- Product use/adherence counseling
- All PK assessments

7.4.3 Participants Who Become Infected with Hepatitis B

All protocol-specified study procedures will continue except:

- Provision of study gel
- Provision of study tablets
- Product use/adherence counseling
- All PK assessments

7.4.4 Participants Who Voluntarily Discontinue Study Gel and/or Tablets

All protocol-specified study procedures will continue except:

- Provision of discontinued study product(s)
- Product use/adherence counseling (if both products are discontinued)
- All PK assessments applicable during the discontinuation period

7.4.5 Participants Who Are Discontinued from Study Gel and/or Tablet Use by the Site Investigator

All protocol-specified study procedures will continue except:

- Provision of discontinued study product(s)
- Product use/adherence counseling (if both products are discontinued)
- All PK assessments applicable during the discontinuation period

7.5 Interim Contacts and Visits

Interim contacts and visits (those between regularly scheduled follow up visits) may be performed at participant request or as deemed necessary by the investigator or designee at any time during the study. Participants will have a urine pregnancy test at each interim visit. All interim contacts and visits will be documented in participants' study records and on applicable case report forms.

Some Interim Visits may occur for administrative reasons. For example the participant may have questions for study staff or require additional study supplies. Other interim contacts and visits may occur in response to AEs experienced by study participants. When interim contacts or visits are completed in response to participant reports of AEs, study staff will assess the reported event clinically and provide or refer the participant to appropriate medical care.

Table 10:	Interim	Visits	and	Contacts
		110110	ana	00111010

Interim Visits and Contacts					
Component	Procedure/Analysis				
Administrative	 Review/update locator information *Schedule next study visit 				
Clinical	 Collect interval medical/menstrual history Review/update concomitant medications Record/update adverse events *Perform physical exam (See Appendix III) *Perform pelvic exam (See Appendix III) *Treat UTI/RTIs/STIs, treat or refer for other findings *Reinforce counseling Contraceptive HIV risk reduction and male condom Product use/adherence Provide HIV pre- and post-test counseling *Provide male condoms, offer panty liners *Provide watch device 				
Urine	 Collect urine sample Qualitative hCG *Dipstick urinalysis (*and culture if positive for leukocyte esterase or nitrates; may omit if culture not standard of care for UTI diagnosis) *SDA for chlamydia and gonorrhea 				
Blood	 *Collect blood specimens *Complete blood count *Liver function tests *Serum chemistries *HIV-1 test (confirmatory testing as needed) *Tenofovir *Syphilis serology (confirmatory testing as needed) *HBsAg 				
Pelvic	 *Collect vaginal pH *Collect vaginal fluid swab for wet mount for BV, Candida, Trichomonas *Collect herpes culture (at sites where standard of care for diagnosis) 				
Study Product Supply	 *Collect any unused study product (gel and/or tablets) *Dispense doses of product(s) 				

7.6 Clinical Evaluations and Procedures

See Appendix III for an outline of physical exam and pelvic exam components.

7.7 Behavioral Measures

The primary behavioral study aims will be addressed using a quantitative instrument and in-depth qualitative interviews (conducted with a subset of study participants). Counts of unused study products, which will be returned to the clinics, also will be compared to reports of adherence.

- 1. The quantitative instrument will be structured around the following topics:
 - Sexual activity
 - Product adherence (frequency and duration of use)
 - Male condom use (frequency and in combination with study products)
 - Timing of sexual activity in relationship to product use
 - Intra-vaginal practices
 - Sharing of study products, including with whom products shared (also selling of products and product theft)
 - Experiences using study products, including obstacles to use, side effects and partner involvement

2. We will identify a random sample of eight participants from five sites (Umkomaas CRS, Botha's Hill CRS, Makerere University-JHU Research Collaboration CRS, Case CRS, and Pitt CRS) to complete an in-depth interview that addresses use of study drugs and male condoms during the trial. These interviews will be conducted by a trained study interviewer and will follow a structured questionnaire guide. They will be approximately 30 minutes in duration and will be conducted at the 21-Week study visit. Participants will be compensated for their completion of the in-depth interview. These interviews will be digitally recorded using a handheld digital voice recorder and this file will be transcribed and translated for analysis.

If, at a particular site, women with differential adherence between study products are not included in the random sample of in-depth interview participants, up to two additional participants from that site, who did report differential adherence between products, will be invited to complete an in-depth interview as well. Reported adherence levels will be monitored by site staff so that eligible women can be identified. These interviews will be conducted within one month of the 21-Week study visit.

The interviews will include the following topics:

- Challenges to use of study products
- Perceived benefits of use
- Preferences between oral and vaginal formulations

- Preferences between a single and dual use regimen
- Partner knowledge of study participation and reaction to product use
- Who knew that they had access to anti-retroviral drugs
- Whether they were ever asked to share (or sell) the product or if someone tried to take it away from them

7.8 Pharmacokinetic Procedures

7.8.1 Pharmacokinetic Procedures: All Participants

During all three study periods (single formulation and dual formulation), participants will provide specimens for PK measures. There are two types of visits that include PK measures: the Mid-Study-Period Visits and the End of Study Period Visits. As noted below and except where limited by site capacity, some PK procedures will be applicable for all participants.

Mid-Study-Period Visits

All participants will provide blood samples for tenofovir levels at Mid-Study-Period Visits (3-Week, 10-Week, and 17-Week). Every effort will be made to record the three doses of tenofovir taken prior to these visits with hour: minute accuracy. These visits do NOT include an observed dose of study product(s) in the study clinic.

End of Study Period Visits

Both US and non-US participants will have an observed dose of study product(s) at these visits.

All participants will provide a blood sample prior to their observed dose of study product(s) at the End of Study Period Visits (6-Week, 13-Week, and 20-Week). This blood sample will be used for:

- Blood tenofovir level
- *At sites with capacity,* cell lysate (intracellular tenofovir diphosphate)
- At sites with capacity, cell counts by flow cytometry. These cell counts serve as surrogate markers for cell activation and proliferation, respectively, and will be used as covariates during intracellular model building.

7.8.2 Pharmacokinetic Procedures: Non-Intensive PK Participants

At non-US sites, participants will take part at End of Study Period Visits (6-Week, 13-Week, and 20-Week) in the collection of samples for a Non-Intensive PK portion of the study.

		PRE-DOSE	POST-DOSE TIMING			
			1-3 HOURS	3-5 HOURS	5-7 HOURS	
Blood: • Flow cytomet sites wit capacity	ĥ l	Study Regimen Sequences A, B, C, D, E, and F				
Blood: PBMC c lysate (intracel tenofovi diphosp (at sites capacity Tenofov	lular r hate) / with	Study Regimen Sequences A, B, C, D, E, and F	Study Regimen Sequences E and F	Study Regimen Sequences A and B	Study Regimen Sequences C and D	
CVL • Tenofov • Proteom and mar inflamm	ics kers of		Study Regimen Sequences E and F	Study Regimen Sequences A and B	Study Regimen Sequences C and D	

For simplicity, Non-Intensive PK Participants will be assigned to a sampling window based on their sequence randomization assignment:

- 1-3 hours, Sequences E and F
- 3-5 hours, Sequences A and B
- 5-7 hours, Sequences C and D

Thus, it is expected that Non-Intensive PK Participants will have one sampling time predose (blood), and only one sampling time post-dose (blood and CVL).

For individual participants, post-dose blood and CVL samples will occur within 15 - 30 minutes of each other (either sample may be taken first). The times of these samples must be recorded with hour: minute accuracy. The same sampling time point (within 15 minutes) in each study period should be used for all of a participant's End of Study Period Visits.

The time of the observed dose(s) of study product(s) administered in clinic and the three prior doses taken must be recorded with hour: minute accuracy. Participants will

receive a small watch or similar timekeeping device to assist them in remembering or recording (on a study-provided form) the times of these doses. An additional device may be provided in the event of a lost or stolen device.

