10.5 Randomization Procedures

Randomization to product sequence will be stratified by site. Within each site, participants will be randomly assigned to one of six study sequences outlined in Table 15: Study Regimen below. In an unblinded trial, special care needs to be taken to assure that the study staff cannot control or guess assignment. The MTN Statistical and Data Management Center will coordinate the randomization procedures, which will be specified in the SSP Manual.

Table 15:	Stuc	dy Re	egimen	

	N	Period 1: 6 WEEKS	1 WK Wash -out	Period 2: 6 WEEKS	1 WK Wash- out	Period 3: 6 WEEKS	1 WK Wash- out
Sequence A	24	Oral		Vaginal		Oral + Vaginal	
Sequence B	24	Vaginal		Oral		Oral + Vaginal	
Sequence C	24	Oral + Vaginal		Oral		Vaginal	
Sequence D	24	Oral + Vaginal		Vaginal		Oral	
Sequence E	24	Oral		Oral + Vaginal		Vaginal	
Sequence F	24	Vaginal		Oral + Vaginal		Oral	

Assignment to end of study period non-intensive PK sample timing will correspond to product sequence randomization for simplicity. For the intensive PK cohorts at domestic sites, the end of study period sample timing will require a second randomization which will be stratified within each of the two sites.

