10.7.2 Primary Analysis

All analyses will be based on data from the 144 evaluable women (women with at least one follow-up visit in each period of the study) after assessing differences in baseline values between the evaluable women and those women lost to follow-up. These differences will be described and used to interpret the generalizability of the results. For the adherence endpoint, the primary analysis will evaluate the difference in product adherence using statistical methods for paired data controlling for period and sequence effects. Prior to this analysis, the presence of any carryover effects will be evaluated using a more liberal alpha level of 10%. Although carryover effects are not expected, if evidence of them is found, we will resort to analyzing only the data from the first period as a simple three arm parallel design using statistical methods for independent data. This will greatly reduce the power of testing. If adherence distributions do not allow the use of parametric tests, rank tests as those described in Koch and Strokes will be used instead.¹³

For the binary acceptability endpoint, similar measures to assess for carryover effects will be used and then for the main outcome, controlling for period and sequence effects, a generalization of McCullagh's proportional odds model for repeated measures will be performed by adding a random effect on the logit scale as proposed by Ezzet and Whitehead.¹⁴ Again, if carryover effects are present, the analysis will only use data from the first period.

Blood and intracellular samples will be analyzed for routine PK parameters - C_{max} , T_{max} , AUC, C_{min} - and described using descriptive statistics. Cervical and vaginal samples will be analyzed using sparse sampling population PK methods to provide PK parameter estimates. Measures of drug exposure (AUC, C_{max}) will be compared between oral and vaginal and dual use concentration differences controlling for sequence and period effects. Post-biopsy blood samples will be evaluated for deviation from expected values. Model building will be attempted to relate blood and intracellular model drug levels if sufficient samples have detectable drug levels.

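### Tying the non-US post-dose sampling window to treatment sequence puts dual use in a single period within each window, which weakens the time-specific dual-versus-single PK contrasts; a separate timing list would avoid this cheaply

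*Protocol*

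**What the plan says.** Section 7.8.2 gives each non-US woman one post-dose sampling time for blood and cervicovaginal lavage (CVL), to be held within 15 minutes across her three End of Study Period Visits. The window follows from her sequence: "Non-Intensive PK Participants will be assigned to a sampling window based on their sequence randomization assignment". The mapping is "1-3 hours, Sequences E and F"; "3-5 hours, Sequences A and B"; "5-7 hours, Sequences C and D". Section 10.5 repeats the rule and its reason: "Assignment to end of study period non-intensive PK sample timing will correspond to product sequence randomization for simplicity".

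The regimen table in section 10.5 fixes the order of treatments, for example "Sequence A 24 Oral Vaginal Oral + Vaginal" and "Sequence B 24 Vaginal Oral Oral + Vaginal".

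At the US sites the pelvic sampling time (pre-dose, 2, 4 or 6 hours) comes from a second randomisation (sections 7.8.3 and 10.5). Section 10.7.2 assigns cervical and vaginal samples to sparse-sampling population PK, and says regimens will be compared on exposure with "concentration differences controlling for sequence and period effects".

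**The concern.** The three pairs of sequences that define the windows are also the three pairs that share a dual-use period. In the non-US cohort, the post-dose time, the sequence pair and the period of dual use are therefore one and the same factor. The dual regimen's time course is assembled from Period 2 data at 1-3 hours, Period 3 data at 3-5 hours and Period 1 data at 5-7 hours. In no period are dual and single samples taken in the same window.

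Comparing systemic and local PK among the three regimens is a primary objective. If concentrations shift between periods, for instance because use of the unobserved doses changes, part of that shift can be taken for the shape of the dual regimen's profile or for a dual-versus-single difference at a particular time. Once samples are taken, the missing combinations cannot be recovered from this cohort.

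**Working it through.** **Inputs.** There are 144 evaluable women, 72 of them at US sites (section 4.3), so 72 are non-US. With equal allocation that is 12 per sequence and 24 per window. Section 10.6 gives five sites 24 women each and two sites 12 each. The three non-US sites can total 72 only at 24 each. The protocol states no figure of its own on this point to reproduce.

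**Layout, from the window list and the regimen table.**

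| Window | Sequences | Dual | Oral | Vaginal |
|---|---|---|---|---|
| 1-3 h | E, F | Period 2 | Periods 1, 3 | Periods 1, 3 |
| 3-5 h | A, B | Period 3 | Periods 1, 2 | Periods 1, 2 |
| 5-7 h | C, D | Period 1 | Periods 2, 3 | Periods 2, 3 |

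**Rank.** The sequence indicators have rank 6, and adding window indicators leaves it at 6. If each sequence is split over the windows, the rank is 8. Regimen-by-window plus period-by-window terms, within woman, have rank 9 under the protocol and 12 when windows are split within sequence.

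**Where period effects enter.** Write p1, p2, p3 for the period effects. The raw within-window contrast, dual minus the mean of oral and vaginal, carries:
- 1-3 h: p2 − (p1 + p3)/2
- 3-5 h: p3 − (p1 + p2)/2
- 5-7 h: p1 − (p2 + p3)/2

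The three terms sum to zero, so the average over windows is free of additive period effects. Each separate window is not.

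**Variances**, in units of the within-woman error variance. Let N be the women observed at a given time and f the share of them who are non-US with aliased timing.
- Balanced timing: 1.5/N.
- Aliased, period effects common to all windows: (1/N)[1/(1 − f²/2) + 1/2].
- Aliased, period effects specific to the window: 1.5/[N(1 − f²)].

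These are the least-squares variances with a separate effect for each woman. They agree with a direct calculation from the design matrices.

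*Non-US cohort alone* (N = 24, f = 1):
- balanced: 1.5/24 = 0.0625;
- aliased, common period effects: (1/24)(2 + 0.5) = 0.1042, a ratio of 1.67;
- aliased, window-specific: 1 − f² = 0, so not estimable;
- averaged over windows, common period effects: 1.5/72 = 0.0208 under either layout.

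Oral versus vaginal within a window has variance 2/24 = 0.083 under either layout.

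*Pooled with US CVL at 2, 4 and 6 hours.* These times are the midpoints of the three windows. Assume 18 US women per time, spread evenly over sequences, with the same time course as non-US women. Then N = 24 + 18 = 42 and f² = (24/42)² = 0.3265:
- balanced: 1.5/42 = 0.0357;
- aliased, common: (1/42)(1.195 + 0.5) = 0.0404, about 13% more;
- aliased, window-specific: 1.5/(42 × 0.6735) = 0.0530, about 48% more.

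*Sensitivity.* The text of section 7.8.3 allows up to 18 women per time, while Table 12 prints 12 per group. With 12, N = 36 and f² = 0.4444. The variances are 0.0417 balanced, (1/36)(1.286 + 0.5) = 0.0496 common (19% more) and 1.5/20 = 0.075 window-specific (80% more).

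**The case against.** The best defence is that the main regimen comparison does not suffer. Each woman keeps one sampling time, so the effect of time cancels in her own regimen differences, and the six sequences are balanced over period. That stands. A reader might infer that dual versus single use is confounded with period in the PK comparison as a whole. The documents do not support this: under additive period effects the averaged contrast has the same variance under both layouts and no bias.

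A reader might also infer that adjusting for sequence, as section 10.7.2 plans, wipes out the post-dose time effect and makes the planned analysis unworkable. That goes too far. The adjustment is stated for comparisons of exposure measures between regimens, and one post-dose sample cannot give a woman her own AUC or maximum by routine methods. The pelvic samples go to population PK, where recorded time since dose can enter the model directly. Nothing says that sequence is a fixed block there.

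The US cohort helps as well. All its women give serial blood samples in every period, so the blood profile does not depend on the non-US windows, and its pelvic times are randomised separately. Section 10.4 discusses sparse sampling for all 144 women, not a stand-alone non-US model. The observed clinic dose, the pre-dose level and the recorded times of the three prior doses let part of any adherence drift be modelled.

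What remains is that these remedies need assumptions: a common time course in US and non-US women, or period effects that do not vary with post-dose time. Separate timing would make the second unnecessary and reduce reliance on the first. The only reason the protocol gives for the mapping is simplicity.

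**Conclusion.** The aliasing is real, and the protocol itself fixes it. Its reach is limited to the dual regimen's post-dose profile and the time-specific dual-versus-single contrasts, chiefly in CVL. The cost is 67% more variance in the non-US cohort alone with common period effects, and non-estimability there if period effects differ by window. After pooling with US data it is about 13% and 48% respectively. The pooled figures rest on 18 US women per time, even spread over sequences and a shared time course. All figures assume equal allocation and a constant within-woman variance. The protocol gives no size for any period effect, so a bias cannot be quantified. The change is worth making because it costs little and serves a primary PK objective, but the trial's overall regimen comparison does not depend on it.

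**What to change.** Assign non-US women to the three windows by a separate randomisation, balanced within sequence across the three non-US sites. Twelve women per sequence gives about 4 per window per sequence. Exact balance within a site is not possible, because 24 women over six sequences is 4 per sequence, which does not divide by three. A 2:1:1 split, with the doubled window rotated over the sites, gives 4 per window in total. Keep the rule that a woman has the same window in all periods. Replace the sequence-to-window mapping in section 7.8.2, Table 11 and section 10.5.

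The cost is one more list of the kind already planned for the US sites and some rewording, with the same visits and samples. Sites would have to look up a woman's window and could no longer read it from her sequence.
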